10. STATISTICAL METHODS

A detailed Statistical Analysis Plan (SAP) will be developed and finalized before the study database is locked which will supersede the statistical analysis methods described in the protocol; however, any major modification of the outcome measures and/or its analysis will also be reflected in the clinical study report (CSR).

Descriptive summaries of variables by treatment will be provided where appropriate. Generally, continuous variables will be summarized using the following descriptive statistics: mean, standard deviation, number of observations, median, minimum, and maximum. Summaries will also be presented for the change from baseline, when appropriate. For categorical variables, the counts and proportions of each value will be tabulated by treatment. For time to event variables, point estimates (25th, 50th, and 75th percentiles) along with 95% confidence intervals will be tabulated by treatment using Kaplan-Meier methods. Survival estimates will also be shown graphically for each treatment.

All statistical tests will be two-sided unless otherwise noted.

The pediatric participants will not be tested, and descriptive statistics will be done on these participants. Additional statistical analyses on these pediatric participants may be provided for specific regulatory requests.

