10.3.9. Primary Efficacy Analysis

The primary analysis will compare the proportion of participants in the adult ITT population who achieve durable platelet response defined as platelet counts at or above 50,000/ μ L for \geq two-thirds of at least 8 non-missing weekly scheduled platelet measurements during the last 12 weeks of the 24-week blinded treatment period in the absence of rescue medication (provided that at least 2 non-missing weekly scheduled platelet measurements are at or above 50,000/ μ L during the last 6 weeks of the 24-week blinded treatment period) between rilzabrutinib and placebo with a Cochran-Mantel-Haenszel test using the two stratification factors at a 2-sided alpha level of 0.05 (see [Appendix 10.7](#) for a description of the primary efficacy analysis in the EU [EEA countries] and UK). Participants who do not respond in the first 12 weeks and enter the open label period will be treated as non-responders in the primary analysis. Participants who discontinue the study due to a rilzabrutinib-related AE lack of efficacy or receive rescue medication (including an increase in allowed concomitant ITP medications dose) will be considered as non-responders. Sensitivity analyses will be conducted on the primary analysis.

The primary endpoint will be analyzed for adult and pediatric participants separately.

Platelet counts conducted locally will be used for the primary endpoint analysis. Platelet counts conducted centrally at Clinic Visits will be used as a back-up for missed or non-analyzable local lab samples.

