## VERSION HISTORY

This statistical analysis plan (SAP) for study EFC17093/PRN1008-018 is based on the amended protocol 03 dated 11 August 2022 (current protocol). This section summarizes the major changes to the statistical analysis features in the SAP including major changes from the current protocol.

The first participant was randomized on 16 April 2021. This SAP is approved before the early analysis is conducted when the last adult participant has concluded the blinded treatment period (see [Section 3.8](#)).

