Primary endpoint (Composite estimand)	
Durable platelet response is defined as the proportion of participants able to achieve platelet counts at or above 50,000/<math>\mu</math>L for <math>\geq</math>two-thirds of at least 8 non-missing weekly scheduled platelet measurements during the last 12 weeks of the 24-week blinded treatment period in the absence of rescue therapy, provided that at least 2 non-missing weekly scheduled platelet measurements are at or above 50,000/<math>\mu</math>L during the last 6 weeks of the 24-week blinded treatment period (Definition 1) b
 
Country-specific definition c : Durable platelet response is defined as the proportion of participants able to achieve platelet counts at or above 50,000/<math>\mu</math>L for at least 8 out of the last 12 weeks of the 24-week blinded treatment period in the absence of rescue therapy (Definition 2)
	ITT	
1) Rescue medication: participants will be considered as non-responders if taking rescue medication after 8 weeks of double-blind treatment and before Week 25 (or last IMP intake, whichever earlier) (composite strategy).
 
2) Discontinuation of study intervention before Week 25 due to lack of response or related adverse events per eCRF: participants will be considered as non-responders (composite strategy).
 
3) Discontinuation of study intervention before Week 25 due to reasons other than the aforementioned: data during the double-blind on-treatment period will be included in the analysis. Post-treatment data will be considered to have had no platelet response (composite strategy)
	
Adults: p-value from Cochran-Mantel-Haenszel (CMH) test adjusted by randomization stratification factors d. Mantel- Haenszel common risk difference and 95% CI based on Mantel-Haenszel stratum weights (1) and the Sato variance estimator (2). Pediatrics: Descriptive.
 
For Definition 2, Missing data due to Covid-19 (per eCRF) are assumed missing at random and will be imputed using the participant's median value of available (a minimum of 3 available required) weekly platelet counts during the last 12 weeks of double-blind on-treatment period. Otherwise, missing data will be considered as no response.

Endpoint Category (estimand)	Estimands			
	Endpoint a	Population	Intercurrent event(s) handling strategy	Population-level summary (Analysis and missing data handling)

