#### *General considerations for efficacy analyses*

The statistical tests will be two-sided tests at a nominal 5% significance level for primary efficacy endpoint and key secondary efficacy endpoints.

Primary and secondary efficacy analyses will be performed in the ITT population, unless otherwise specified. The analyses of primary and key secondary endpoints are to compare the rilzabrutinib treatment group and the placebo treatment group.

The study primary and key secondary efficacy analyses will be based on the adult population at the time when the last adult participant has completed the 24-week blinded treatment period. The results based on the adults at the early analysis will be considered as final and serve as the basis

for registration application submissions. A separate analysis for the pediatric population will be similarly performed after pediatric participants have completed the blinded treatment period which may be at the same or different time when the adults have completed the blinded treatment period. The efficacy analyses on the pediatric population will be descriptive. Final analysis will be performed at the completion of the study. Additional analyses (eg, OL and LTE parts) may be performed before the final analysis. Please refer to [Section 3.8](#) for more details.

The randomization stratification factors will include splenectomy status (yes, no) and severity of thrombocytopenia (platelet counts  $<15,000/\mu\text{L}$ ,  $\geq 15,000/\mu\text{L}$ ).

For platelet count, a scheduled measurement will be used if it is available. Otherwise, an unscheduled measurement will be allocated to a scheduled visit if it is within the analysis window of the scheduled visit (see details in [Section 5.4](#)).

Rescue medications are recorded in eCRF by the investigator. Per protocol, rescue medications include IVIg, high-dose CSs, platelet infusion, and anti-D immunoglobulin infusion intended to increase platelet counts or prevent bleeding when platelet counts are less than  $20,000/\mu\text{L}$ , or for bleeding or wet purpura. Other rescue medications are not permitted.

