#### 3.2.1 Definition of endpoint(s)

Please refer to [Section 1.2.2.1](#) for primary efficacy endpoint.

To qualify for a durable responder (Definition 1, [Section 1.2.2.1](#)), a participant must have met ALL of the following criteria:

- At least 8 non-missing weekly platelet measurements during the last 12 weeks of the 24-week treatment period, and
- Platelet counts  $\geq 50,000/\mu\text{L}$  for  $\geq$ two-thirds of the 8 non-missing weekly assessments above, and
- At least 2 platelet counts  $\geq 50,000/\mu\text{L}$  occurred during the last 6 weeks of the 24-week treatment period, and
- Not rescued after 8 weeks of treatment and before Week 25 (or last IMP intake, whichever earlier). A participant who is rescued during this period will be considered as a non-responder, and
- Not discontinued before Week 25 due to related TEAE (per investigator's assessment) or lack of response. A participant who discontinues before Week 25 and the reason for discontinuation is treatment related adverse event (AE) or lack of response will be considered as a non-responder.

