**Table 5 - Tipping Point Analysis: Durable Platelet Response Status**

Definition	Criteria (during the last 12 weeks of DB on-treatment period)	Status
Definition 1 a	Rescued after 8 weeks of treatment and before Week 25	Non-responder
	Discontinued before Week 25 due to related TEAE or lack of response	Non-responder
	Observed non-responder: $\geq 5$ weekly platelet counts $< 50,000/\mu\text{L}$	Non-responder
	Observed responder:	Responder
	1. $\geq 8$ weekly platelet counts $\geq 50,000/\mu\text{L}$ , OR 2. 6 or 7 weekly platelet counts $\geq 50,000/\mu\text{L}$ in total out of $\geq 8$ non-missing weekly platelet counts among which $\geq 2$ weekly platelet counts $\geq 50,000/\mu\text{L}$ out of last 6 weeks	
	Undetermined: due to missing data, or discontinuation not due to related AE or lack of response	Missing
Definition 2 b	Rescued after 8 weeks of treatment and before Week 25	Non-responder
	Discontinued before Week 25 due to related TEAE or lack of response	Non-responder
	Observed non-responder: $\geq 5$ weekly platelet counts $< 50,000/\mu\text{L}$	Non-responder
	Observed responder: $\geq 8$ weekly platelet counts $\geq 50,000/\mu\text{L}$	Responder
	Undetermined: due to missing data, or discontinuation not due to related AE or lack of response	Missing

a Definition 1. Durable platelet response defined as a proportion of participants able to achieve platelet counts at or above  $50,000/\mu\text{L}$  for  $\geq$  two-thirds of at least 8 non-missing weekly scheduled platelet measurements during the last 12 weeks of the 24-week blinded treatment period in the absence of rescue therapy, provided that at least 2 non-missing weekly scheduled platelet measurements are at or above  $50,000/\mu\text{L}$  during the last 6 weeks of the 24-week blinded treatment period. Definition 1 not applicable to countries within the EU (EEA countries) and UK.

b Definition 2. Durable platelet response defined as a proportion of participants able to achieve platelet counts at or above  $50,000/\mu\text{L}$  for at least 8 out of the last 12 weeks of the 24-week blinded treatment period in the absence of rescue therapy. Definition 2 applicable to countries within the EU (EEA countries) and UK only.

TEAE = treatment emergent adverse event.

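### The SAP does not carry the protocol rule that a raised background steroid or TPO-RA dose counts as rescue and so as non-response on the primary endpoint

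*SAP*

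**What the plan says.** Protocol 10.3.9 states that participants who "receive rescue medication (including an increase in allowed concomitant ITP medications dose) will be considered as non-responders". Appendix 10.7 repeats this for the EU and UK primary analysis, so it covers both definitions of durable response. The permitted background medications are an oral corticosteroid (CS) and/or a TPO-RA.

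SAP 3.1 gives the working definition of rescue. It says "Rescue medications are recorded in eCRF by the investigator" and then "Per protocol, rescue medications include IVIg, high-dose CSs, platelet infusion, and anti-D immunoglobulin infusion". A dose increase is not named. The scoring rules refer to rescue only:

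- Table 2 and 3.2.2, first intercurrent event: "participants will be considered as non-responders if taking rescue medication after 8 weeks of double-blind treatment and before Week 25".
- 3.2.1, Definitions 1 and 2: "Not rescued after 8 weeks of treatment and before Week 25 (or last IMP intake, whichever earlier").
- Table 5, tipping-point status: "Rescued after 8 weeks of treatment and before Week 25".

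Protocol Section 10 provides for a SAP "which will supersede the statistical analysis methods described in the protocol". The SAP's version history says that it "summarizes the major changes to the statistical analysis features in the SAP including major changes from the current protocol". Neither its Table 1 nor Table 11 in 3.9 mentions removal of the dose-increase rule.

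**The concern.** Raising a steroid or TPO-RA dose can itself lift the platelet count, which is what the primary endpoint measures. The protocol deals with this by scoring such a participant as a non-responder. A programmer working from the SAP has no instruction to do so. The same event can therefore be non-response under the protocol and response under the SAP, and nothing shows that anyone chose this.

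The gap is narrower than all dose increases. A large steroid increase may be captured as high-dose CS, and any increase that the investigator enters as rescue is already non-response. What remains is a TPO-RA increase, or a modest CS increase, that is not entered as rescue.

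**Working it through.** **1. Where the rule appears.**

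| Place | Dose increase scored as rescue? |
|---|---|
| Protocol 10.3.9 | Yes |
| Protocol Appendix 10.7 (EU, UK) | Yes |
| Protocol Synopsis, primary efficacy analysis | No |
| Protocol rescue lists (Synopsis study design, Section 4, 6.6.1) | No |
| SAP 3.1, Table 2, 3.2.1 (both definitions), 3.2.2, Table 5 | No |
| SAP Table 1 and Table 11 (records of changes) | Removal not listed |

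The protocol is itself uneven, and the SAP's four options match its operational lists. The SAP is based on Amendment 03 and the protocol in hand is Amendment 05, but the change summaries for Amendments 04 and 05 do not list this rule as added.

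**2. Who can be affected.** A participant must be on background CS or TPO-RA; have the dose raised, although doses must stay stable and the Synopsis, Section 4 and 9.3.5 allow only reductions for safety (6.6.2 says adjustments); not have the increase entered as rescue; remain in the blinded period past Week 13; and still meet the platelet criteria over the last 12 weeks.

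**3. The plan's own power.** Inputs from SAP Section 4: 129 and 65 adults, 25% versus 5%, Fisher's exact test, two-sided 0.05. Summing over all tables (a, b) with a/129 > b/65 and two-sided Fisher p < 0.05:

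power = Σ Bin(a; 129, p1) × Bin(b; 65, p0)

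At p1 = 0.25 and p0 = 0.05 this is 96.4%, consistent with the stated 95%.

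**4. Effect under assumed rates.** The documents give no frequency of dose increases, so the rate r is an assumption. Take 25% and 5% as the rates under the protocol rule and add r for participants whom the SAP would score as responders despite an increase.

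| r | Same rate of 129 | Equal rates: SAP rates | Difference | Power | Placebo only: SAP rates | Difference | Power |
|---|---|---|---|---|---|---|---|
| 0 | 0 | 25.0% v 5.0% | 20.0 | 96% | 25% v 5.0% | 20.0 | 96% |
| 1/65 = 1.5% | 2 | 26.5% v 6.5% | 20.0 | 94% | 25% v 6.5% | 18.5 | 91% |
| 2/65 = 3.1% | 4 | 28.1% v 8.1% | 20.0 | 92% | 25% v 8.1% | 16.9 | 83% |
| 3/65 = 4.6% | 6 | 29.6% v 9.6% | 20.0 | 90% | 25% v 9.6% | 15.4 | 72% |

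The last row is a generous upper end. The assumed placebo rate is about 3 responders (0.05 × 65 = 3.25), so three more nearly doubles it.

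**5. False positives.** With no true effect and equal rates in both arms (5% + r in each), the chance of a significant result favouring rilzabrutinib is 1.2%, 1.3% and 1.4% for the three rates, against 0.9% at r = 0. All are below the nominal one-directional 2.5% (0.05/2).

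Fisher's test is used because the plan's sample size uses it. The main test is Cochran-Mantel-Haenszel, so the figures are indicative.

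**The case against.** The SAP introduces its list as coming from the protocol and leaves rescue to investigator entry. On that reading a dose increase is a form of rescue, and one entered as such is already non-response. This stands for increases that are entered. Whether sites would enter them depends on the eCRF, which is not in the documents, and a list of four therapies gives them no prompt to do so.

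Increases are barred during blinded treatment, so each case would be a protocol deviation. That also stands and is why the number should be small. But the protocol wrote a scoring rule for the event all the same, and the SAP's summary of major deviations does not rescore anyone.

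Participants who have not responded by Week 13 leave the blinded period, and the SAP expects high dropout on placebo, so fewer than 65 placebo participants can be affected. This makes the 72% figure a pessimistic bound.

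SAP 3.2.4 repeats the primary analysis by concomitant ITP medication. Participants with no background therapy have no dose to raise, so that subgroup partly shows whether the effect holds without the problem. It does not settle how the others are scored in the main analysis.

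**Conclusion.** The two documents conflict on who counts as a primary responder, and no change is recorded. The practical effect is probably small. Under the assumed rates, balanced misclassification costs two to six points of power and leaves the difference intact; misclassification on placebo alone would be conservative but could cost more. With no such cases nothing changes. These results rest on assumed rates of 1.5% to 4.6% and on the planned 25% versus 5%.

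A reader might infer two stronger things. The first is that the SAP deliberately reversed the rule, or will count every dose increase as response. The documents show silence, not reversal, and recorded rescue still counts. The second is that the omission inflates the chance of a false positive for rilzabrutinib. That would need increases concentrated on rilzabrutinib when the drug has no effect, and under blinding the documents offer no reason for that.

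**What to change.** In SAP 3.1, Table 2, 3.2.1 (both definitions), 3.2.2 and Table 5, state that an increase in concomitant CS or TPO-RA dose above baseline counts as rescue and so as non-response, in the window the SAP already uses for rescue: after 8 weeks of treatment and before Week 25 or last study drug intake, whichever is earlier. Protocol 10.3.9 sets no window for dose increases, so this is a choice to be stated. Because 3.1 also feeds the key secondary endpoints, say whether the addition applies to them or to the primary endpoint only, which is where the protocol places it.

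Derive the event from the concomitant medication records rather than from rescue entries, after confirming that the eCRF holds dated doses. Tabulate such increases by arm. Align the primary analysis text in the protocol Synopsis with 10.3.9. If the rule was dropped on purpose, record that with the reason instead.

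The cost is one criterion repeated in five places, one table, a little programming, and possibly a few more non-responders.

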Appendix 10.7 EU (EEA countries) and UK-specific requirements

Synopsis, Section 3.1 Objectives, Section 3.1.1 Efficacy Objectives, Section 3.2 Endpoints, Section 10.3.9 Primary Efficacy Analysis; In the UK and countries within the EU (EEA countries):

- The primary endpoint in the blinded treatment period is the proportion of participants able to achieve platelet counts at or above 50,000/ μ L for at least 8 out of the last 12 weeks of the 24-week blinded treatment period in the absence of rescue therapy.
- The primary efficacy analysis is as follows: The primary analysis will compare the proportion of participants in the adult ITT population who achieve durable platelet response defined as platelet counts at or above 50,000/ μ L for ≥ 8 out of the 12 scheduled observations in the last 12 weeks of the 24-week blinded treatment period in the absence of rescue medication between rilzabrutinib and placebo with a Cochran-Mantel-Haenszel test using the two stratification factors at a 2-sided alpha level of 0.05. Participants who do not respond in the first 12 weeks and enter the open label period will be treated as non-responders in the primary analysis. Participants who discontinue the study due to a rilzabrutinib-related AE, lack of efficacy or receive rescue medication (including an increase in allowed concomitant ITP medications dose) will be considered as non-responders. Sensitivity analyses will be conducted on the primary analysis.
- In the blinded treatment period, the following is a key secondary objective: To evaluate the change from baseline in IBLS.

- In the blinded treatment period, the following is a key secondary efficacy endpoint (the last endpoint in the multiplicity control): Change from baseline in IBLS assessment at Week 25
- Key secondary efficacy analysis: Compare the change from baseline in IBLS assessment at Week 25

EU (EEA countries) only

Throughout the protocol, the allowed age range for pediatric participants is ≥ 10 to < 18 years, where permitted by local regulation.

Synopsis and Section 5.1, Inclusion criterion 1:

Participants will be male and female with primary ITP with duration of > 6 months in pediatric participants aged ≥ 10 to < 18 years (where allowed by local regulation) and duration of > 3 months in adults ≥ 18 years.

Synopsis and Section 5.1, Inclusion criterion 3:

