### 3.2.2 Main analytical approach

The main analysis of the primary endpoint is to compare the responder rate of the rilzabrutinib treatment group with the placebo treatment group via the primary estimand as defined in [Table 2](#).

To reject the null hypothesis of no treatment difference, the two-sided p-value based on a Cochran-Mantel-Haenszel (CMH) test adjusted by randomization stratification factors ([Section 3.1](#)) must be  $<0.05$  in the adult ITT population. The Mantel-Haenszel estimate of common risk difference in response rates and its associated 95% confidence interval based on Mantel-Haenszel stratum weights (1) and the Sato variance estimator (2) will be reported. The observed response rate for each treatment group will be presented along with its associated 95% asymptotic confidence interval (CI).

For pediatric participants, the observed response rate will be calculated along with its associated (90% and 95%, respectively) CI in each treatment group using the Clopper-Pearson exact method. The difference in response rate and its associated 95% exact CI will be presented.

For Pharmaceuticals and Medical Devices Agency (PMDA) in Japan, the consistency of efficacy in pediatric population will be assessed with Method 2: the difference in response rate in the pediatric population is in the same direction as that in the adult population (ie, the response rate in rilzabrutinib group is numerically higher than that in the placebo group in the pediatric population) given that the treatment effect in adults is significant (ie,  $p\text{ value} < 0.05$ ).

Graphical presentations of the results will be provided as needed. SAS® sample code could be found in [Section 5.7](#).

**Intercurrent events** will be handled with the primary estimand specified in [Table 2](#). Specifically,

1. Rescue medication: participants will be considered as non-responders if taking rescue medication after 8 weeks of double-blind treatment and before Week 25 (or last IMP intake, whichever earlier) (composite strategy).

2. Discontinuation of study intervention before Week 25 due to lack of response or related AE (per investigator's assessment in eCRF): participants will be considered as non-responders (composite strategy).

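### The SAP leaves out the protocol rule that a dose increase in allowed concomitant ITP medication makes a participant a non-responder on the primary endpoint, and does not declare the omission

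*SAP*

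**What the plan says.** Protocol 10.3.9, on the primary analysis, says that participants who "receive rescue medication (including an increase in allowed concomitant ITP medications dose) will be considered as non-responders". Appendix 10.7, which sets the EU (EEA) and UK version of the endpoint, repeats the parenthesis: "including an increase in allowed concomitant ITP medications dose". The rule therefore applies to both definitions of durable response.

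SAP 3.1 describes rescue as what the investigator records in the eCRF and adds: "Per protocol, rescue medications include IVIg, high-dose CSs, platelet infusion, and anti-D immunoglobulin infusion". It says that other rescue medications are not permitted. In SAP Table 2 the first intercurrent event reads: "participants will be considered as non-responders if taking rescue medication after 8 weeks of double-blind treatment and before Week 25". Section 3.2.1 makes "Not rescued after 8 weeks of treatment and before Week 25 (or last IMP intake, whichever earlier") one of the criteria that must all be met, and gives the same condition for the EU/UK definition. Section 3.2.2 and Table 5 use matching wording ("participants will be considered as non-responders if taking rescue medication after 8 weeks of double-blind treatment"; "Rescued after 8 weeks of treatment and before Week 25"). None of these places mentions a dose increase.

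The SAP's version history says that it "summarizes the major changes to the statistical analysis features in the SAP including major changes from the current protocol". Table 1, which follows, has no entry on this point. Nor does Section 3.9 with Table 11.

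**The concern.** The two documents give different scoring rules for the primary endpoint. Protocol section 10 lets the SAP supersede its methods, and the synopsis makes the SAP the final authority while expecting it to address changes of substance. As written, the SAP's shorter rule would govern without a stated decision to drop the protocol's rule.

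A TPO-RA increase, or a corticosteroid increase short of high dose, fits none of the SAP's four rescue classes. Either can raise platelets independently of study drug. If it is not entered as rescue, the participant can meet every SAP criterion for durable response. The exposure is limited to participants who stay in blinded treatment past Week 13, since earlier non-responders are scored as such. Those who stay are the only ones who can become durable responders, and few are expected on placebo. Settling the question after unblinding would be a post hoc decision about the primary endpoint.

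**Working it through.** **1. Text comparison**

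| Place | Dose increase counts as rescue? |
|---|---|
| Protocol 10.3.9 | Yes |
| Protocol Appendix 10.7 (EU/UK) | Yes |
| Protocol synopsis (primary analysis), 3.2.1, and the rescue lists in 4 and 6.6.1 | Not mentioned |
| SAP 3.1, Table 2, 3.2.1 (both definitions), 3.2.2, Table 5 | Not mentioned |
| SAP Table 1; Section 3.9 and Table 11 | No change declared |

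Timing does not readily explain the gap. SAP version 3 (18 March 2024) is based on protocol amendment 03. The change tables for amendments 04 and 05 do not list the rule as added, so it was very probably already in amendment 03, although that text is not supplied. Amendment 05 (15 May 2024) still carries it.

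**2. Inputs and the plan's own figure.** SAP section 4 gives 129 vs 65 adults, 25% vs 5%, two-sided 0.05, Fisher's exact test and 95% power. Power is the sum, over all pairs of responder counts, of Bin(x; 129, p₁) × Bin(y; 65, p₀) for the pairs that are significant. At 25% vs 5% this gives 96.4% for Fisher, consistent with the stated 95%. For the CMH test with a single stratum (chi-square with N−1 variance) it gives 97.3%. The planned CMH uses two stratification factors whose distribution is not given, so one stratum is an approximation.

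Expected responders: 0.05 × 65 = 3.25 on placebo and 0.25 × 129 = 32.25 on active.

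**3. Illustration A: false responders added to true rates of 25% and 5%.** The rates are 0.05 + k/65 on placebo and, for the equal-rate case, 0.25 + 2k/129 on active.

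| Added cases | Fisher | CMH, one stratum |
|---|---|---|
| none | 96.4% | 97.3% |
| 1 / 2 / 3 in placebo only | 91.0 / 82.6 / 71.8% | 92.9 / 85.8 / 76.2% |
| same rate: 1 / 2 / 3 placebo with 2 / 4 / 6 active | 94.3 / 92.2 / 90.2% | 95.7 / 94.0 / 92.3% |

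**4. Illustration B: false responders in the active arm only.** Suppose the SAP count gives 25% vs 5%, but a share f of the active responders had a dose increase. The protocol's rate is then 25% × (1 − f), or 22.5%, 20.0% and 17.5% for f = 10%, 20% and 30%. Fisher power at those rates is 91.7%, 82.7% and 68.5%, against 96.4% on the SAP count. Here the SAP count would flatter the drug.

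**5. Sensitivity to single cases.** With 3, 4, 5 or 6 placebo responders, the smallest significant active count is 20, 22, 25 or 27 (Fisher), or 18, 21, 24 or 27 (CMH, one stratum). Each extra placebo responder raises the bar by 2 or 3.

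The values of k and f are assumptions. The documents give no frequency of dose increases.

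**The case against.** - **Increases are already prohibited.** Doses must stay stable from 14 days before Day 1. Protocol section 4 allows only reductions, for safety, and 9.3.5 says the same of standard-of-care medication. An increase is thus a protocol deviation and probably uncommon. This stands as a limit on size. It does not remove the conflict, because the protocol still attaches a scoring consequence. A reader might infer from the word for dose changes in 6.6.2, which is neutral as to direction, that increases for safety are allowed. Read with section 4 and 9.3.5, the protocol does not support that.
- **The rule may operate through the eCRF.** The protocol treats an increase as a kind of rescue, so a site might record it as such. That would catch some cases, but the SAP's four-class list gives no assurance for a TPO-RA or modest corticosteroid increase. Nor does SAP 5.3, which presents rescue and concomitant ITP medication in separate summaries, show that increases escape the rescue records. The eCRF instructions are not supplied.
- **The protocol is itself uneven.** Its synopsis and its own rescue lists lack the clause, so the SAP's list copies one part of the protocol and misses another. This is fair, and it argues for clarification rather than blame. The clause is nonetheless explicit in both regional descriptions of the primary analysis.
- **Disclosure is partly covered.** Protocol section 10 says that major modifications will be reflected in the study report. That comes after the analysis and does not settle the rule before it.

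**Conclusion.** The conflict is real and concerns a rule of the primary endpoint, for both definitions. It should be resolved before database lock. Its numerical effect is unknown and probably small.

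Two stronger readings are tempting. One is that the omission favours rilzabrutinib. The documents do not show this: false responders on placebo would dilute the contrast, those on active would inflate it, and no frequency by arm is given. The other is that the trial loses its power. The 72% figure needs three false responders, all on placebo. With the same rate in both arms power stays at or above 90%, and the planned sample size is unaffected. What stands is that few placebo responders are expected, so a handful of cases could matter, and their scoring is currently undefined.

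**What to change.** In SAP Table 2, 3.2.1, 3.2.2 and Table 5, for both definitions, extend the rescue criterion with words such as: *including an increase above baseline dose of allowed concomitant CS or TPO-RA*. Keep the SAP's existing window: after 8 weeks and before Week 25 or last study-drug intake, whichever is earlier. Identify cases from the concomitant-medication records, which the Schedule of Assessments already collects at clinic visits, in a blinded review before lock.

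Alternatively, list the removal as a change from the protocol, with a reason, and run the protocol rule as a sensitivity analysis.

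Counting a newly started CS or TPO-RA is an optional extension, since the protocol speaks only of a dose increase. The key secondary endpoints need no change.

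The cost is SAP wording and one blinded medication review, with no new data collection. The downside is that a few participants may lose responder status.
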